6.2.4.1 Guidelines for the follow-up of laboratory hematologic abnormalities

In case of any occurrence of febrile neutropenia, neutropenia \geq grade 3 or thrombocytopenia \geq grade 3, tests must be performed weekly (or more frequently if clinically indicated) until the event resolves to \leq grade 2. Subsequent monitoring must be performed every 4 weeks. See [Table 6-4](#).

6.2.4.2 Guidelines for the follow-up of laboratory liver abnormalities

In patients with any clinically relevant laboratory liver abnormality, as defined below, hepatic toxicity monitoring must include ALL of the following liver function tests (LFTs): albumin, ALT, AST, total bilirubin (fractionated if total bilirubin $> 2.0 \times$ ULN), alkaline phosphatase and GGT). Note: for patients with Gilbert Syndrome, total and direct bilirubin must be monitored, but intensified monitoring applies to changes in direct bilirubin only.

In case of any occurrence of ALT/AST/total bilirubin increase to grade 2 the LFTs must be monitored weekly (or more frequently if clinically indicated) until the event resolves to \leq grade 1. Thereafter monitoring must be continued every other week (or more frequently if clinically indicated) for two additional cycles (e.g. 8 weeks). If there is no recurrence of grade 2 ALT/AST/total bilirubin elevations during this period, subsequent monitoring must be performed every 4 weeks.

In case of any occurrence of ALT/AST/total bilirubin increase to grade 3 or 4, LFTs must be monitored weekly (or more frequently if clinically indicated) until the event resolves to \leq grade 1. Thereafter monitoring must be continued every other week (or more frequently if clinically indicated) for four additional cycles (e.g. 16 weeks). If there is no recurrence of \geq grade 2 ALT/AST/total bilirubin elevations during this period, subsequent monitoring must be performed every 4 weeks. For patients with liver metastasis and grade 2 AST/ALT at baseline, increased monitoring is required for grade 3/4 AST/ALT; follow guidelines for grade 3 or 4 AST/ALT.

Patients who discontinue study treatment due to liver toxicity must be monitored weekly (or more frequently if clinically indicated) until the event resolves to \leq grade 1 or stabilization occurs (no CTCAE grade change over 4 weeks). Refer to [Table 6-4](#).

Patients with transaminase increase combined with total bilirubin (TBIL) increase may be indicative of potential DILI, and should be considered as clinically important events.

The threshold for potential DILI may depend on the patient's baseline AST/ALT and TBIL value; patients meeting any of the following criteria will require further follow-up as outlined below:

- For patients with normal ALT and AST and TBIL value at baseline: AST or ALT $> 3.0 \times$ ULN combined with TBIL $> 2.0 \times$ ULN

- For patients with elevated AST or ALT or TBIL value at baseline: [AST or ALT > 2 x baseline AND > 3.0 x ULN] OR [AST or ALT > 8.0 x ULN], combined with [TBIL > 2 x baseline AND > 2.0 x ULN]

Medical review needs to ensure that liver test elevations are not caused by cholestasis, defined as: ALP elevation > 2.0 x ULN with R value (ALT/ALP in x ULN) < 2 in patients without bone metastasis, or elevation of ALP liver fraction in patients with bone metastasis.

Note: (The R value is calculated by dividing the ALT by the ALP, using multiples of the ULN for both values. It denotes the relative pattern of ALT and/or ALP elevation is due to cholestatic or hepatocellular liver injury).

In the absence of cholestasis, these patients should be immediately discontinued from study drug treatment, and repeat LFT testing as soon as possible, preferably within 48 hours from the awareness of the abnormal results. The evaluation should include laboratory tests, detailed history, physical assessment and the possibility of liver metastasis or new liver lesions, obstructions/compressions, etc.

- Laboratory tests should include ALT, AST, albumin, creatinine kinase, total bilirubin, direct and indirect bilirubin, GGT, prothrombin time (PT)/INR and alkaline phosphatase.
- A detailed history, including relevant information, such as review of ethanol, concomitant medications, herbal remedies, supplement consumption, history of any pre-existing liver conditions or risk factors, should be collected.
- Further testing for acute hepatitis A, B, C or E infection and liver imaging (eg, biliary tract) may be warranted.
- Obtain PK sample, as close as possible to last dose of study drug, if PK analysis is performed in the study.
- Additional testing for other hepatotropic viral infection (CMV, EBV or HSV), autoimmune hepatitis or liver biopsy may be considered as clinically indicated or after consultation with specialist/hepatologist.

All cases confirmed on repeat testing meeting the laboratory criteria defined above, with no other alternative cause for LFT abnormalities identified should be considered as “medically significant”, thus, met the definition of SAE (Section 8.2.1) and reported as SAE using the term “potential drug-induced liver injury”. All events should be followed up with the outcome clearly documented.

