Data analysis	Using the PAS, PK concentration versus time profiles of LDK378 will be summarized separately for patients with extensive PK assessment and patients with sparse PK sampling. The mean and individual concentration versus time profiles of LDK378 will be displayed graphically for full PK profile and trough collections. LDK378 PK parameters, including but not limited to AUClast, AUC0-24h, AUCinf, Cmax, Tmax, Lambda z, terminal T1/2, T1/2,acc, Racc, CL/F (or CLss/F at steady state) and Vz/F, as appropriate will be derived from PK run-in patients with extensive PK assessment. All PK parameters will be summarized. The PK parameters and concentration data will be listed Safety data including adverse events, vital signs, ECG and laboratory abnormalities will be summarized and listed. For efficacy, ORR as assessed by investigator will be estimated and the binomial exact 95% CI provided. DOR will be listed by patient and described using Kaplan-Meier methods and relevant statistics. DCR will be estimated and the binomial exact 95% CI provided. PFS, and OS will be described using Kaplan-Meier methods and appropriate summary statistics. Efficacy data will be listed. [REDACTED] [REDACTED] [REDACTED]
Key words	ALK, NSCLC, LDK378

Amendment 3

Amendment rationale

As of 29-Sep-2015, of 103 patients treated, 66 patients have been discontinued from treatment and 37 are still receiving study treatment.

The amendment provides follow up evaluations for hepatic toxicities and work-up guidelines for potential Drug Induced Liver Injury (DILI) cases in order to optimize patient safety.

Other change was implemented in this amendment: Dose guidance modification for QTc text is being updated to provide clarification on monitoring procedure.

Changes to the protocol

Changes to specific sections of the protocol are shown in the track changes version of the protocol using strike through red font for deletions and red underlined for insertions.

The following sections to the protocol were changed:

- List of abbreviations updated with commonly used abbreviations
- Table 6-3: “Refer to Section 6.2.4.2 for additional follow-up” was added for AST or ALT and concurrent Total bilirubin management. Follow-up description updated for Grade 3 QTc interval prolonged.
- Section 6.2.4.2: Updated on following up evaluations for hepatic toxicities and work-up guidelines for potential Drug Induced Liver Injury (DILI) cases to align with Novartis Oncology trial standard language.

IRB/IEC

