Total Bilirubin** (for patients with Gilbert Syndrome these dose modifications apply to changes in direct [conjugated] bilirubin only)	
Grade 1 ($> ULN$ and $\leq 1.5 \times ULN$)	Maintain dose level with liver function test (LFTs)*** monitored as per protocol
Grade 2 (> 1.5 and $\leq 3.0 \times ULN$) with ALT or AST $\leq 3.0 \times ULN$	Omit dose until resolved to \leq Grade 1, then: If resolved in ≤ 7 days, then maintain dose level If resolved in > 7 days, then $\downarrow 1$ dose level
Grade 3 (> 3.0 and $\leq 10.0 \times ULN$) with ALT or AST $\leq 3.0 \times ULN$	Omit dose until resolved to \leq Grade 1, then: If resolved in ≤ 7 days, $\downarrow 1$ dose level If resolved in > 7 days discontinue patient from LDK378

Worst toxicity (CTCAE 4.03 Grade)*		Dose Modifications for LDK378
Grade 4 ($> 10.0 \times \text{ULN}$)		Permanently discontinue patient from LDK378
AST or ALT		
Grade 1 ($> \text{ULN}$ and $\leq 3.0 \times \text{ULN}$)		Maintain dose level with LFTs*** monitored per protocol
Grade 2 (> 3.0 and $\leq 5.0 \times \text{ULN}$) without total bilirubin elevation to $> 2 \times \text{ULN}$		Maintain dose level with LFTs*** monitored per protocol
Grade 3 (> 5.0 and $\leq 20.0 \times \text{ULN}$) without total bilirubin elevation to $> 2 \times \text{ULN}$		Omit dose until resolved to \leq Grade 1, then $\downarrow 1$ dose level
Grade 4 ($> 20.0 \times \text{ULN}$) without total bilirubin elevation to $> 2.0 \times \text{ULN}$		Omit dose until resolved to \leq Grade 1, then $\downarrow 1$ dose level
AST or ALT and concurrent Total bilirubin		
AST or ALT $> 3.0 \times \text{ULN}$ with total bilirubin $> 2.0 \times \text{ULN}$ in the absence of cholestasis or hemolysis		Permanently discontinue patient from LDK378 Refer to Section 6.2.4.2 for additional follow-up
PANCREATIC		
Amylase and/or lipase elevations (in the absence of clinical symptoms)		
Grade 1 ($> \text{ULN}$ and $\leq 1.5 \times \text{ULN}$)		Maintain dose level
Grade 2 ($> 1.5 - 2.0 \times \text{ULN}$)		Maintain dose level
Grade ≥ 3 ($> 2.0 \times \text{ULN}$)		Omit dose until resolved to \leq Grade 1, then $\downarrow 1$ dose level
Note: Withhold ceritinib for acute onset of new or progressive unexplained abdominal symptoms, such as severe pain or vomiting; perform diagnostic procedures (e.g., abdominal CT scan or ultrasound) to exclude pancreatic pathology.		
RENAL		
Serum creatinine		

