Grade 3 Grade 4 (in patients taking a concomitant medication also known to cause bradycardia or a medication known to cause hypotension)	Omit dose until recovery to asymptomatic bradycardia or to a heart rate ≥ 60 bpm If the concomitant medication can be adjusted or discontinued, resume LDK378 at $\downarrow 1$ dose level with frequent monitoring
Grade 4 (in patients who are not taking a concomitant medication also known to cause bradycardia or known to cause hypotension)	Permanently discontinue LDK378.

* Common Terminology Criteria for Adverse Events (CTCAE) version 4.03. All dose modifications should be based on the worst preceding toxicity.
 ** If Grade 3 or 4 hyperbilirubinemia is due to the indirect (non-conjugated) component only, and hemolysis as the etiology has been ruled out as per institutional guidelines (e.g., review of peripheral blood smear and haptoglobin determination), then $\downarrow 1$ dose level and continue treatment at the discretion of the Investigator.
 ***LFTs include albumin, ALT, AST, total bilirubin, alkaline phosphatase and GGT
 **** Dose modifications apply to patients who experience diarrhea despite appropriate antidiarrheal medication. This medication should be started at the first sign of abdominal cramping, loose stools or overt diarrhea (see [Section 6.3.2.5](#))
 ***** Dose modifications apply to patients who experience nausea and/or vomiting despite appropriate antiemetic medication. This medication should be started at the first sign of nausea and/or vomiting (see [Section 6.3.2.6](#))

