6.2.4 Follow-up for toxicities

An unscheduled visit should be performed in all cases below where toxicity monitoring is recommended more frequently than defined by the schedule of assessments ([Table 7-1](#)).

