7.1.2 Screening

Written informed consent must be obtained before any study specific procedure is performed. Screening assessments to confirm eligibility into the main study should be performed as per the schedule of assessments. Patients that do not have available documentation of ALK rearrangement at Screening must wait for result of the ALK rearrangement status before initiating treatment with LDK378.

Re-screening of patients will not be allowed, but laboratory parameters which do not meet the inclusion criteria may be re-tested within the screening window (Day -28 to Day -1). Laboratory assessments performed as part of the screening evaluations will not be required to be repeated prior to dosing (except urine pregnancy test). The cardiac eligibility criteria should be assessed with the central ECG report. Tumor imaging assessments will be performed at screening between Day -28 and Day -1. Any imaging assessments already completed during the regular work-up of the patient within 28 days prior to start of treatment, including before signing the main study ICF can be considered as the baseline images for this study.

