7.2.2.5 Laboratory evaluations

Central laboratories will be used for the analysis of scheduled hematology, biochemistry and other blood specimens collected as part of safety monitoring (as detailed in [Table 7-1](#)). Dipstick urinalysis will be performed locally, except in the case of any out of range parameter on scheduled local urinalysis, when a urine sample will be sent to central laboratory for further analysis. Laboratory values obtained during the Screening phase will be used to assess patient's eligibility. The time windows granted for laboratory evaluations are identical to the corresponding visit time windows for each visit (refer to [Section 7.1](#)).

The site does not need to wait for the results of centrally-analyzed laboratory assessments when an immediate clinical decision needs to be made and in those cases locally unscheduled testing may be performed.

Details on the collection, shipment of samples and reporting of results by the central laboratory are provided to investigators in a separate [\[Laboratory Manual\]](#).

Table 7-3 Clinical laboratory parameters collection plan

Test Category	Test Name
Hematology	Hemoglobin, platelets, white blood cells (WBC), red blood cells (RBC), differential (basophils, eosinophils, lymphocytes, monocytes, neutrophils [% or absolute])
Blood Chemistry	Albumin, ALT, AST, calcium (at screening calcium corrected for albumin in addition to calcium), creatinine, creatinine clearance, total bilirubin, direct bilirubin (only if total bilirubin is \geq grade 2), blood urea nitrogen (BUN) or urea, magnesium, potassium, sodium, fasting glucose, phosphate (inorganic phosphorus), alkaline phosphatase, amylase, lipase, GGT
Urinalysis	Macroscopic Panel (Dipstick) (Color, bilirubin, Blood, Glucose, Ketones, Leukocyte esterase, nitrite, pH, protein, specific gravity, urobilinogen) Microscopic panel (RBC, WBC, casts, crystals, bacteria, epithelial cells)
Pregnancy	At screening visit, serum pregnancy test At subsequent cycles, urinary pregnancy test (dipstick). If local requirements dictate otherwise, local regulations should be followed
Hormones (males only)	Testosterone (total and free), LH, FSH, sex hormone binding globulin (SHBG)
Coagulation	INR and pro-thrombin time (PT) or Quick Test

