2.4 Study design

This is a phase I/II, open-label, multi-center study to assess the PK, safety, tolerability and efficacy of LDK378 in adult Chinese patients with locally advanced or metastatic NSCLC harboring a confirmed ALK rearrangement. Patients must have demonstrated progression during or after crizotinib treatment whether or not previously treated with cytotoxic chemotherapy and have no available ALK-targeted treatment options.

Overall approximately 100 patients will be enrolled in the study. The first 15 enrolled patients will enter a 5-day PK run-in period during the phase I component of this study. They will have PK sampling over 120-hour during the run-in period following a single oral dose at 750 mg. Additional patients may be enrolled in the study with the 5-day PK run-in period in case PK profiles from some of the enrolled patients are deemed not evaluable

The phase II component of the study will start on Cycle 1 Day 1 for all enrolled patients. During this period LDK378 will be given as continuous daily oral dosing at 750 mg QD in 28 -day cycles.

[figure not shown]
Extensive PK assessment will be collected for the first 15 enrolled patients to obtain approximately 12 evaluable full profiles. Sparse PK samples will be collected for the rest of patients. Adverse events will be collected at every visit after informed consent obtained. Laboratory assessment including hematology and blood chemistry will be taken at screening, run-in Day 1 for the first 15 enrolled patients, Day 1, Day 8, Day 15 for cycle 1 and Day 1 for subsequent cycles. Separate ECG monitoring schedules will also be collected for patients with extensive PK assessment and those with sparse assessment.

[figure not shown]
Tumor response will be evaluated every 8 weeks (i.e. every 2 cycles) starting from the first day of treatment with LDK378 until the time of RECIST-defined Progressive disease (PD) by investigator assessment, withdrawal of consent for further follow-up, loss to follow-up or death. This schedule of tumor assessment will continue regardless of dose interruptions. For patients who discontinue treatment in the absence of progression, tumor assessments will continue every 8 weeks until progression of disease, withdrawal of consent for further follow-up, loss to follow-up or death.

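### For Gilbert patients the bilirubin rules act on direct bilirubin, but Table 7-3 schedules it only once total bilirubin is grade 2 or higher; the SAP's direct bilirubin shift table depends on the same conditional test (minor)

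*Protocol*

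**What the plan says.** **Rules.** In Table 6-3 the total bilirubin block carries the note "for patients with Gilbert Syndrome these dose modifications apply to changes in direct [conjugated] bilirubin only". Protocol 6.2.4.2, on follow-up of laboratory liver abnormalities, adds that "for patients with Gilbert Syndrome, total and direct bilirubin must be monitored, but intensified monitoring applies to changes in direct bilirubin only".

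**Collection.** The chemistry row of Table 7-3 includes "direct bilirubin (only if total bilirubin is", and the condition that follows is grade 2 or above. Table 6-3 puts grade 2 at > 1.5 x ULN. Table 7-3 makes no exception for Gilbert patients or for screening. The liver panel defined in the Table 6-3 footnotes does not contain direct bilirubin.

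**Visits.** SAP 2.4 says that hematology and chemistry "will be taken at screening, run-in Day 1 for the first 15 enrolled patients, Day 1, Day 8, Day 15 for cycle 1", and then on Day 1 of later cycles. Protocol 7.1.2 adds: "Laboratory assessments performed as part of the screening evaluations will not be required to be repeated prior to dosing" (the urine pregnancy test is the exception).

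**Entry.** Under inclusion criterion 5, patients without Gilbert syndrome need total bilirubin < 1.5 x ULN. Gilbert patients need total < 3.0 x ULN or direct < 1.5 x ULN, so a direct value is an alternative and not a requirement.

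**Analysis.** SAP 3.2.9.2 names direct bilirubin among the biochemistry parameters to be summarized, and plans shift tables from baseline to worst post-baseline value. SAP 3.1.1.6 takes the last assessment on or before first dose as baseline and lets unscheduled values count.

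**The concern.** A dosing and monitoring rule should act on something that the visit schedule supplies. For Gilbert patients the rules replace total bilirubin with direct bilirubin, but the schedule still uses total bilirubin to decide whether direct is measured. At total <= 1.5 x ULN the site has no scheduled value of the analyte that governs its decision and must order the test on its own initiative.

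The SAP output is a separate consequence of the same conditional test. A shift table needs a baseline and a follow-up value from a recognizable population. Here most patients would have neither, and the scheduled follow-up values would come from patients selected for raised total bilirubin. SAP 3.2.1 takes percentages over the relevant population, so the result could be misread as a rate for all treated patients.

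**Working it through.** The plan gives no figure to reproduce. The check sets the rules against each other and adds some simple arithmetic.

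**1. Rule against collection, by level of total bilirubin**

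| Total bilirubin | Direct scheduled by Table 7-3? | Analyte used for a Gilbert patient |
|---|---|---|
| <= 1.5 x ULN | No | Direct |
| > 1.5 x ULN | Yes | Direct |

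A Gilbert patient who enters above 1.5 x ULN is covered from screening. One at or below that level is not.

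**2. Samples on which the test could be run (SAP 2.4, six cycles)**

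- Screening 1 + Cycle 1 Days 1, 8 and 15 = 3 + Day 1 of Cycles 2 to 6 = 5, total 9.
- With the PK run-in Day 1 sample: 9 + 1 = 10.
- If the first-dose-day sample is not repeated (protocol 7.1.2): 8 and 9.

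So 8 to 10 samples are drawn, and none gives a scheduled direct value while total stays at or below 1.5 x ULN.

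**3. Could a dose step be missed at total <= 1.5 x ULN?**

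Let T be total bilirubin in multiples of its ULN, f the direct fraction of total, and r the ratio of direct ULN to total ULN.

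- Multiples read against the total ULN: direct = f x T. Since f <= 1 and T <= 1.5, direct <= 1.5 and the grade 2 step (> 1.5) cannot be crossed.
- Multiples read against direct bilirubin's own ULN: direct = f x T / r. The step is crossed when f > 1.5 x r / T, which at T = 1.5 is f > r.

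The documents do not give r. For an assumed range of 0.2 to 0.4, the direct fraction at T = 1.5 would have to exceed 20% to 40%. Whether a step can be missed therefore depends on which ULN is meant, and the protocol does not say. Criterion 5 states a direct limit beside a separate total limit, which is consistent with direct having its own ULN but does not settle how Table 6-3 should be read.

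**4. What would populate the SAP table**

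- Baseline: an eligible non-Gilbert patient has total < 1.5 x ULN at the qualifying test, and the reflex test needs > 1.5 x ULN. The ranges do not overlap, so that test yields no direct value. A baseline can still arise from an earlier screening value at grade 2 that was retested lower, a pre-dose Day 1 sample that triggers the reflex test, or an unscheduled or local test (SAP 3.1.1.6, 3.2.9.2).
- After baseline: scheduled direct values exist only for patients whose total exceeds 1.5 x ULN.

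The documents do not allow an estimate of how many patients the table would contain.

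**5. Reach of a protocol change**

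The Amendment 3 rationale states: "As of 29-Sep-2015, of 103 patients treated, 66 patients have been discontinued from treatment and 37 are still receiving study treatment". That is 37/103 = 35.9%. Recruitment was already complete by Amendment 2, so a change at Amendment 3 could reach only the Gilbert patients among those 37. Their number is not stated.

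**The case against.** The strongest reply is that the design fits together. Every bilirubin step in Table 6-3 is a multiple of ULN. Where this protocol wants a comparison with baseline it says so, as it does for creatinine and for potential DILI with abnormal starting values. The word change in the Gilbert notes can then be read as naming the analyte to grade, so a first direct value is usable without a baseline. The reflex test begins where the first dose action begins, and Gilbert patients entering above 1.5 x ULN, who most need the exemption, are covered. A Table 6-3 footnote starts from the grade and then asks whether "hyperbilirubinemia is due to the indirect (non-conjugated) component only", which suits a reflex test. Section 6.2.4 also provides: "An unscheduled visit should be performed in all cases below where toxicity monitoring is recommended more frequently than defined by the schedule of assessments".

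Much of this stands. The lack of a baseline does not stop the rule from working, and on the total-ULN reading no step is missed. It does not remove the mismatch. The footnote concerns grades 3 and 4 and is not specific to Gilbert patients. Unscheduled visits follow an abnormality already found. The sentence on monitoring total and direct either applies only to patients under follow-up, and so schedules nothing beforehand, or is a general duty that Table 7-3 does not carry out.

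On the SAP it is fair to say that direct bilirubin is not among the liver tests singled out there (total bilirubin, ALT, AST and ALP), that all data will be listed anyway (SAP 3.2.9), and that no decision rests on this table.

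**Conclusion.** A minor point that holds, with medium confidence. For Gilbert patients at total bilirubin <= 1.5 x ULN, the analyte that governs dose modification and intensified monitoring is not scheduled. The planned direct bilirubin shift table will have few baselines and a selected set of follow-up values.

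A reader might infer three stronger things that the documents do not support:

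- That the Gilbert rules cannot be applied without a direct baseline. They can, because the steps are multiples of ULN.
- That dose steps will be missed. This needs the multiples to refer to direct bilirubin's own ULN, and the numerical range above rests on an assumed r.
- That no non-Gilbert patient can have a direct baseline. Such baselines should be rare, but the routes in step 4 exist.

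The stop for raised AST or ALT with total bilirubin, the DILI work-up and the main liver summaries are unaffected. The conclusion assumes that the laboratory rows and footnotes of Table 7-1, missing from the available text, contain no Gilbert note. The number of Gilbert patients is unknown and may be zero.

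**What to change.** - **Table 7-3:** for patients with Gilbert syndrome, collect direct bilirubin at screening and at every chemistry visit, on the sample already drawn. For patients already enrolled this means the remaining visits, which restores monitoring but cannot create a baseline.
- **Table 6-3:** state whether the Gilbert multiples refer to the ULN of direct or of total bilirubin.
- **Section 6.2.4.2 (editorial):** fractionation is required there above 2.0 x ULN, but from grade 2 in Table 7-3. Use grade 2 in both; following the lower cut-off already meets both.
- **SAP 3.2.9.2:** replace the direct bilirubin shift table with the number of patients tested and a listing of direct with same-date total bilirubin. Use patients tested as the denominator for any percentage.

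Cost: wording in three places of the protocol, at most 8 to 10 extra assay results per Gilbert patient over six cycles with no extra blood draw, and one descriptive table exchanged for a count and a listing that is largely planned already.
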